## 5.2.5. Management of Toxicity Related to Seribantumab

In the event that a patient experiences a toxicity  $\geq$  Grade 3 that is not an IRR and is possibly, probably or definitively related to seribantumab treatment, and not related to fulvestrant, it is at the investigator's discretion to hold dosing or discontinue treatment with seribantumab. Prior to holding the dose or discontinuing treatment, the investigator must notify the sponsor and Medical Monitor.

In the event that seribantumab treatment has been held for 28 consecutive days, the patient should be discontinued. No dose reductions for seribantumab are permitted.

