# 9.4.2. Relatedness to Study Drug

The investigator must attempt to determine if there exists reasonable possibility that an adverse event is related to the use of one or more study drugs, according to the following guidelines:

- Unrelated: This category is applicable to those AEs that are clearly due to extraneous causes (concurrent drugs, environment, etc.) and/or the clinically plausible temporal sequence is inconsistent with the onset of the event and the administration of the study drug and do not meet the criteria for drug relationship listed under UNLIKELY, POSSIBLY, PROBABLY, DEFINITELY RELATED or UNKNOWN.
- Unlikely: The event is clearly due to causes distinct from the use of the study drug, such as a documented pre-existing condition, the effect of a concomitant medication a new condition which, based on the pathophysiology of the condition, and the pharmacology of the study drug, would be unlikely related to the use of the study drug
- **Possible:** The event follows a reasonable temporal sequence from administration of the study drug AND the event follows a known pathological response pattern to the study drug BUT the event could have been produced by an intercurrent medical condition which, based on the pathophysiology of the condition, and the pharmacology of the study drug, would be unlikely related to the use of the study drug or the event could be the effect of a concomitant medication
- **Probable:** The event follows a reasonable temporal sequence from administration of the study drug and the event follows a known response pattern to the study drug AND the event cannot have been reasonably explained by an intercurrent medical condition or the event cannot be the effect of a concomitant medication
- **Definite**: The event follows a reasonable temporal sequence from administration of the study drug, the event follows a known response pattern to the study drug and based on the known pharmacology of the study drug, the event is clearly related to the effect of the study drug
- Unknown: Based on the evidence available, causality cannot be ascribed

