#### 10.5.4. Safety Analyses

Safety analyses (adverse events and laboratory analyses) will be performed using the safety population. Adverse events will be coded using the latest MedDRA dictionary. Severity of adverse events will be graded according to the NCI CTCAE version 4.03.

Treatment-emergent adverse events (TEAEs) are defined as any event that occurred after the first dose of study drug and was not present prior to study drug administration or worsened in severity after study drug administration. TEAEs will be collected through the end of treatment visit. Frequency and percent summaries will be presented for treatment-emergent adverse events (TEAE) defined as adverse events that occur or worsen in severity following the first dose of seribantumab, or fulvestrant. Additional tabulations include serious adverse events (SAE), TEAE-related to seribantumab, fulvestrant and TEAE grade  $\geq 3$ , and discontinuation due to TEAE. Adverse events will be summarized by System Organ Class and preferred term. All adverse event data will be listed by patient.

Maximum and minimum decrease in continuous laboratory data will be reported. Bar graphs depicting treatment arms will be reported. Frequency and percent of abnormal laboratory values (L/ULN, 2\*L/ULN) will be assessed. Shift to most severe toxicity grade will be summarized.

Vital signs, ECG, and ECHO/MUGA will be tabulated for the change from baseline by time point. Additional analyses may be performed as described in detail within the SAP.

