## **3.6.1** Treatment-Emergent Adverse Events (TEAE)

Adverse events will be considered treatment-emergent if:

- The event occurs for the first time after the start of study treatment and on or before 30 days after final dose of study treatment and was not observed prior to start of treatment
- The event was observed prior to the start of treatment but increased in NCI CTCAE v4 grade during study treatment

The eCRF will capture TEAEs on the adverse event page, while those events occurring pre-treatment will be captured on medical history.

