## 4.3 Safety Data

Missing adverse event, vital sign, ECG, or laboratory data will be considered missing in summary analyses.

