#### 5.6.2 Adverse Events

Adverse events will be coded using the latest MedDRA dictionary at the time of coding. NCI CTCAE v4.0 will be used to grade severity. Frequencies and percentages will be reported by System Organ Class (SOC) and preferred term (PT). Patients with multiple events for a category will be counted once in the highest CTCAE classification. Summary tables will include treatment-emergent AEs, unless specified otherwise. Treatment-emergent adverse events (TEAEs) will be defined as patients based on the event onset date relative to first dose of study drug in the study. Missing onset date for an event will be considered as TEAE. Adverse events with a starting date 30 or more days after the last dose date are not considered TEAEs. Relatedness will be considered: Possibly, Probably, or Definitely related per case report form classification. If relatedness is missing the adverse event will be considered TEAE. The order of reporting the events in summary tables will be according to the following where applicable:

- SOC will be alphabetically reported
- Descending order of frequencies according to the number of patients in the seribantumab treatment group experiencing an adverse event
- PT will be alphabetically reported

The following tables will be reported:

- TEAE
  - Any TEAE by SOC
  - Any TEAE by SOC and PT\*
  - Any TEAE by PT
  - Any TEAE by PT by NCI CTCAE Grade
  - Any TEAE by PT by cycle

- Any TEAE by PT by NCI CTCAE Grade by cycle
- Related TEAE
  - Any TEAE by SOC and PT\*
  - Any TEAE by PT
  - Any TEAE by PT by NCI CTCAE Grade
- TEAE NCI CTCAE Grade 3 or higher
  - Any TEAE by SOC and PT
  - Any TEAE by PT
- Related TEAE NCI CTCAE Grade 3 or higher
  - Any TEAE by SOC and PT
  - Any TEAE by PT
- SAE TEAEs only
  - Any SAE by SOC and PT\*
  - Any SAE by PT
- TEAE Various
  - Any TEAE Resulting in Dose Reduction
  - Any TEAE Resulting in Treatment Discontinuation
  - Any TEAE Resulting in Death

In the AE preferred term summary tables, a patient having multiple events within a System Organ Class is counted only once for that SOC. Similarly, a patient having multiple events under a preferred term is counted only once for that PT. Listings will be provided for all adverse event data.

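### The SAP's rule for missing relatedness sets treatment-emergent status instead of relatedness, and the protocol's Unknown category is unmapped, so the related-TEAE tables may be understated

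*SAP*

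**What the plan says.** SAP 5.6.2 defines which causality ratings count as related: "Relatedness will be considered: Possibly, Probably, or Definitely related per case report form classification". The next sentence handles missing ratings: "If relatedness is missing the adverse event will be considered TEAE". The same paragraph treats an event with a missing onset date as treatment-emergent, and says that an event starting 30 or more days after the last dose is not. The section then lists three tables of related TEAEs and two of related TEAEs of grade 3 or higher.

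SAP 3.6.1 defines treatment-emergence by timing or by worsening in grade. Its first limb reads: "The event occurs for the first time after the start of study treatment and on or before 30 days after final dose". Relatedness plays no part. SAP 4.3 gives the general rule for gaps in safety data: "Missing adverse event, vital sign, ECG, or laboratory data will be considered missing in summary analyses".

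Protocol 9.4.2 has six causality categories: Unrelated, Unlikely, Possible, Probable, Definite and Unknown. It describes Unknown as follows: "Based on the evidence available, causality cannot be ascribed". Its definition of Unrelated confirms that Unknown is a category of its own, since such events must "do not meet the criteria for drug relationship listed under UNLIKELY, POSSIBLY, PROBABLY, DEFINITELY RELATED or UNKNOWN". Protocol 10.5.4 requires related-event tables ("Additional tabulations include serious adverse events (SAE), TEAE-related to seribantumab, fulvestrant") but does not say which categories count as related.

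**The concern.** Whether an event is treatment-emergent depends on when it began or worsened. Whether it is related is a separate judgement by the investigator. A rule that answers a missing causality judgement by declaring the event treatment-emergent leaves the actual question open, namely whether the event enters the related tables. It may also change an attribute that was already settled.

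Safety of the combination is a secondary objective (Protocol 2.2), and Protocol 1.5.3.1 says that seribantumab has not been combined with fulvestrant in other clinical studies. The related tables are not the only safety output, but they are prespecified. A programmer following the signed text should not have to guess how to treat an undetermined causality rating. Any loss from these tables goes one way: leaving such events out can only lower the related counts.

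**Working it through.** No sample size, power or alpha figure depends on this rule, so the plan has no figure to reproduce. The check is a comparison of texts, followed by a statement of scale.

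1. **An event with missing relatedness that starts inside the window.** It is already treatment-emergent under SAP 3.6.1, so the missing-relatedness sentence adds nothing. It is not Possibly, Probably or Definitely related, and SAP 4.3 leaves the rating missing. It therefore appears in the all-causality tables and is absent from the five related tables (3 + 2).

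2. **An event with missing relatedness that starts after the window.** Such events are collected. Protocol 9.2 requires reporting through the first survival follow-up contact, and later if the investigator judges the event related. Protocol 6.6 puts that contact 2 months after the 30-day visit. By the window sentence in SAP 5.6.2 the event is not treatment-emergent; by the missing-relatedness sentence it is. The paragraph contradicts itself.

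3. **An event with missing relatedness that starts before dosing.** SAP 3.6.1 sends pre-treatment events to medical history, so they would not normally reach the rule. Protocol 9.2, however, puts events on the adverse event page from informed consent. This route is open only to the extent that those two sections conflict.

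4. **An event rated Unknown.** The rating is not missing, so the missing-relatedness sentence does not apply. It is not on the SAP's list of three, so it falls outside the related tables by default, although the protocol calls it neither related nor unrelated.

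5. **Scale.** Inputs: 80 patients randomized 1:1 (Protocol 10.2), so 80 / 2 = 40 per arm. The number of missing or Unknown ratings is not given in the documents and is an assumption here. Let k be the number of patients in an arm whose only events under a term have missing or Unknown causality. The related row is then lower than under a rule that counts them by 100 × k / 40 percentage points:

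| k | Shortfall (percentage points) |
|---|---|
| 0 | 0.0 |
| 1 | 2.5 |
| 2 | 5.0 |
| 4 | 10.0 |

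The unit is patients because SAP 5.6.2 counts a patient once per preferred term. A patient with another related event under the same term stays in the row.

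**The case against.** The strongest reply is that TEAE is a slip of the pen for related. The sentence follows directly on the list of related categories and mirrors the missing-onset rule in the same paragraph. On that reading the sponsor already intended the conservative rule for missing ratings. This is plausible, but the signed text does not deliver that intent, and the Unknown gap remains.

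Second, the three-category grouping has support in the protocol. Protocol 5.2.5 speaks of toxicity "possibly, probably or definitively related to seribantumab treatment". That section concerns treatment decisions, however, and does not say how undetermined causality is to be tabulated.

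Third, the SAP relies on the case report form, which is not supplied. SAP 1 names protocol 02-03-10, and SAP 1.2 describes a phase 3 trial with exemestane or fulvestrant. The form behind this SAP may have no Unknown option. This stands, and the Unknown part of the point is conditional on it.

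Fourth, the all-causality tables keep treatment-emergent events of this kind, and in a double-blind, placebo-controlled trial the comparison between arms in those tables does not depend on attribution. This also stands and limits the consequence.

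A reader might go further and infer that the related tables *are* biased low. That needs two things the documents do not supply: that missing or Unknown ratings occur, and that they ought to count as related. The second is a conservative convention, not a protocol requirement. Nor can an assumed share of events be turned into a bias in these tables, because they count patients.

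**Conclusion.** The point holds as an error in an operative rule, with a modest and uncertain effect. The missing-relatedness sentence in SAP 5.6.2 sets the wrong attribute, contradicts the window in its own paragraph for late events, and does not place events with missing causality in the related tables, from which SAP 4.3 would leave them out. Unknown is unmapped and, if the form offers it, falls outside those tables by default.

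The related-TEAE and related grade 3 or higher tables may therefore be understated. The size cannot be computed from the documents. It is zero if no such events occur, and 2.5 percentage points per affected patient in an arm of about 40. That figure assumes about 40 treated patients per arm and a convention under which missing or Unknown counts as related. In the other direction, the literal sentence could add out-of-window events to the overall TEAE count.

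A reader might also infer that treatment-emergence should be fixed by dates alone. The documents do not support that: SAP 3.6.1 and Protocol 10.5.4 both count pre-existing events that worsen, and a dates-only rule would drop them.

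**What to change.** Before database lock, make three changes to SAP 5.6.2.

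- Replace the missing-relatedness sentence with: *If relatedness is missing, a treatment-emergent event will be counted as related (to each study drug for which the assessment is missing) in the related-TEAE tables.* Naming the drug matters because Protocol 10.5.4 plans relatedness to seribantumab and to fulvestrant.
- State how Unknown is handled: in the same way, or as a separate row or sensitivity table. Check the categories against the case report form and Protocol 9.4.2.
- Determine treatment-emergent status only by the onset-or-worsening definition in SAP 3.6.1, with no reference to relatedness. In doing so, align the boundary day: SAP 3.6.1 includes an event starting 30 days after the final dose, and SAP 5.6.2 excludes it.

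The cost is a few sentences of SAP text. The downside is that related-event rates may become slightly higher; a separate row for undetermined causality would let readers see how much of the rate comes from it.

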## 5.6.3 Laboratory Evaluation

Laboratory analytes will be summarized according to panel (i.e., hematology, chemistry, urinalysis).

Shift in laboratory analyte grade will be characterized by worst from baseline and at end of treatment. Shift categories will include normal grade 1 to grade 5 and totals. Percentages will be based on the number with baseline and postbaseline values for that particular analyte.

## 5.6.4 Vital Signs

Vital sign parameters: systolic and diastolic blood pressure (mmHg), respiratory rate (breaths per minute), body temperature (C°), weight (kg) and pulse rate (beats per minute) will be summarized by observed and change from baseline according to minimum and maximum values. Additionally the frequency and percentage of patients for each observed parameter outside the normal range during treatment (up to 30 days post last dose date) will be reported.

Parameter	Units	Normal Range
Systolic Blood Pressure	mmHg	90 - 180
Diastolic Blood Pressure	mmHg	50 - 105
Pulse Rate	Beats per minute	50 - 120
Respiratory Rate	Breaths per minute	12 - 25

#### Table 5.6.4.1 Vital Signs Normal Range

## 5.6.5 Electrocardiogram

The number and percentage of patients with worst ECG result as order: Abnormal, Clinically Significant, Abnormal, not Clinically Significant, Normal will be summarized at screening. Results will be counted once for each patient and scheduled visit.

Exposure-Response Analysis: The relationship between seribantumab plasma concentration and  $\Delta QTcF$  (changefrom-baseline QTcF) will be quantified using a linear mixed effects model with  $\Delta QTcF$  as the dependent variable, plasma concentration as continuous covariate, and treatment (active or placebo) and time as categorical factors, and a random intercept and slope per subject. The geometric mean of the individual Cmax values for subjects on seribantumab will be determined. The predicted effect and its two-sided 90% CIs for  $\Delta\Delta QTcF$  (placebo-corrected change-from-baseline QTcF) at this geometric mean Cmax will be obtained.

By-Timepoint Analysis: The analysis for QTcF will be based on a linear mixed effects model with ΔQTcF as the dependent variable, baseline QTcF as covariate, and time (categorical), treatment (seribantumab and placebo), and time by treatment interaction as factors. An unstructured covariance matrix will be specified for the repeated measures at post-dose timepoints within subject. If the model with unstructured covariance matrix fails to converge, other covariance matrix such as compound symmetry can be considered. For this analysis a 90% 2-sided confidence interval (CI) will be calculated for the contrasts " seribantumab - placebo" for each time point, separately. For change-from-baseline as well as the placebo-corrected change-from-baseline HR, PR, and QRS, descriptive analysis including number of subjects, mean, median, min, max, standard deviation (SD), standard error (SE), and 90% confidence interval (CI; from t-distribution) will be calculated for each treatment and timepoint.

Categorical Analysis: The analysis results for categorical outliers and T-wave morphology will be summarized in frequency tables with counts and percentages for both number of subjects and number of timepoints. For categorical outliers, the number (percentage) of subjects as well as timepoints with increases in QTcF from baseline of >30 and >60 msec and absolute QTcF values >450, >480, and >500 msec; increase in PR interval from baseline >25% and a PR interval >200 msec; increase in QRS interval from baseline >25% and a QRS interval >120 msec; decrease in HR from baseline >25% and a HR <50 bpm; and increase in HR from baseline >25% and a HR >100 bpm will be determined by each treatment group, respectively. For T-wave morphology, the analysis will be focused on the treatment-emergent changes.

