# 6. Schedule of Assessment

# **6.1.** Schedule of Assessments: Heregulin Positive Patients

Procedure Screening Visit		Cycle 1 				Cycle 2 				Additional Cycles 				Every 8 weeks	30 Day	Every 2 months
	Wk 1	Wk 2	Wk 3	Wk 4	Wk 1	Wk 2	Wk 3	Wk 4	Wk 1	Wk 2	Wk 3	Wk 4	from first dose 	Follow -Up 	from FU Visit	
Informed Consent	X															
HRG Testing	$X^1$															
Tumor Biopsy 	X															
Medical history	$X^1$															
Demographics	X 															
Vital signs	$X^2$	X		X		X		X		X		X			X	
ECOG PS	$X^2$	X				X				X					X	
CBC	$X^2$	X		X		X		X		X		X			X	
Serum chemistry	$X^2$	X		X		X		X		X		X			X	
Coagulation profile	$X^2$	X				X				X					X	
Pregnancy test	$X^2$														X	
ECG	X 	$X^{16}$				$X^{16}$				$X^{16}$						
ECHO/MUGA 	$X^1$													X	$X^{20}$	
Archived tumor, if available	X															
Fresh tumor biopsy	$X^{11}$															
Serum for seribantumab PK 		$X^{7a}$		$X^{7b}$		$X^{7b}$		$X^{7b}$								
Serum for Ig 		X				X				X					X	
Serum for biomarkers 		X				X				X						
Plasma for ESR1 testing		$X^{21}$													X	
Plasma for fulvestrant PK		$X^{12}$		$X^{12}$		$X^{12}$		$X^{12}$								
Concomitant meds	$X^1$	X		X		X		X		X		X			X	
Seribantumab dosing		X		X		X		X		X		X				
Fulvestrant dosing		X		X		X				X						
SAE/AE assessment and reporting 							•	Continuo	us monito	oring						
Hospitalization reporting 		X		X		X		X		X		X			X	X
Disease evaluation 	$X^1$													X 	X	
Overall Survival Reporting																$X^{15}$

Proprietary and Confidential Page 43 of 65

-  Procedures to be completed within 28 days of signing the **main** informed consent form
-  Procedures to be completed within 7 days of first dose of Seribantumab
-  Two independent readings at least 5 minutes apart
-  Evaluations may be performed  $\pm$  1 week from the scheduled date of visit
-  Any patient that comes off treatment for reasons other than progressive disease, will have a scan to assess disease status at the time of treatment discontinuation and additional scans every 8 weeks (+/- 1 week) until investigator-assessed PD
-  All procedures should occur ±2 calendar days from scheduled date of visit

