-  Seribantumab PK: all patients; in relation to seribantumab infusion
  - a C1W1: immediately after the end of the Seribantumab infusion (+15 mins)
  - b C1W3, C2W1, C2W3: pre-dose
-  Immunogenicity samples should be collected for all patients prior to dosing.
-  In the event a patient experiences an infusion reaction at any point in the study, an anti-Seribantumab antibody assay will be taken within 24 hours of the event, in addition to the scheduled time-points. For patients who experience a Grade 3 or 4 infusion reaction to Seribantumab, an anti-Seribantumab antibody titer will be taken as close to the onset of the infusion reaction as possible, at the resolution of the event and 28 days (+/- 2 days) following the event.
-  Disease evaluation per RECIST version 1.1.
-  Tumor sample is to be collected for all HRG positive patients that receive HRG results for eligibility based on testing of archived samples. An additional sample is not required for patients who underwent a fresh biopsy for eligibility testing.
-  Fulvestrant PK: all patients: prior to seribantumab injection
-  Serum for biomarkers should be collected pre-infusion on week 1 of each cycle for all patients
-  End of treatment (30-day Follow-up) visit should be completed within 30 days of the last dose of study drug
-  Should patients refuse or drop out of survival follow-up, attempts should be made to obtain any death information available via public records.
-  One reading prior to infusion with seribantumab.
-  AE/SAE collection to be included. S/AE assessment and reporting will proceed as outlined in Sections 9.2 and 9.3
-  All patient hospitalizations and/or hospital visits should be collected, whether or not associated with an adverse event.
-  In addition to the timepoints noted, MUGA or Echocardiogram should be performed post-screening for any study patient who develops symptoms consistent with new onset of congestive heart failure.
-  Unless performed within the last 4 weeks as part of assessments in the previous cycle
-  Sample to be collected prior to any study treatment.

Proprietary and Confidential Page 44 of 65

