## 3.6.2 Laboratory, ECG, and Vital Signs Data

Assessments will be assigned to cycles based on the collection date of the sample relative to the start dates of the cycles from the study drug administration page.

Baseline assessments will be considered as those data collected:

- Within 28 days prior to first day of study drug and
- The closest non-missing data value assessment prior to the first dose date

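### The exposure-response model for change in QTcF omits baseline QTcF, which the by-timepoint model in the same section includes; this costs precision but does not bias the comparison

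*SAP*

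**What the plan says.** SAP 5.6.5 sets out two mixed models with change in QTcF as the outcome. The exposure-response model has "plasma concentration as continuous covariate, and treatment (active or placebo) and time as categorical factors, and a random intercept and slope per subject". Its result is the predicted placebo-corrected change at the geometric mean Cmax, with a 90% interval. The by-timepoint model has "baseline QTcF as covariate, and time (categorical), treatment (seribantumab and placebo), and time by treatment interaction as factors", and "For this analysis a 90% 2-sided confidence interval (CI) will be calculated for the contrasts" between seribantumab and placebo at each time point. The section gives no reason for treating baseline differently in the two models. The categorical analysis counts "increases in QTcF from baseline of >30 and >60 msec", along with absolute QTcF thresholds.

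SAP 3.6.2 defines the ECG baseline as a value within 28 days before first study drug, and specifically as "The closest non-missing data value assessment prior to the first dose date". SAP 3.8, on covariates, allows a Cycle 1 Day 1 value if the procedure comes before dosing. Neither section mentions averaging.

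The schedule in Protocol 6.1 asks for "Two independent readings at least 5 minutes apart" at screening and, in week 1 of each cycle, "One reading prior to infusion with seribantumab". A patient therefore has three untreated readings by the first infusion.

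The SAP introduction names protocol seribantumab-02-03-10, and SAP 1.3 lists an ECG objective. The protocol supplied is MM-121-02-02-10. It has no ECG objective, and its section 10.5.4 only tabulates ECG change from baseline by time point.

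**The concern.** Change in QTcF is a later reading minus the baseline reading, so measurement error in the baseline enters the outcome with a negative sign. Patients whose baseline is high by chance tend to show a fall, and those whose baseline is low by chance a rise. If the arms happen to differ at baseline, part of that difference passes into the treatment term unless baseline is in the model. The random intercept does not replace the covariate: it absorbs between-patient spread in the changes but makes no use of the observed baseline.

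The treatment term is part of the predicted contrast at Cmax, so its precision matters. The supplied protocol plans only 80 randomised patients (Protocol 10.2). A further source of noise is that the baseline is one reading when three are scheduled, and the error of that one reading is carried into every later change for the patient.

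**Working it through.** Neither document gives a QTcF SD, an ECG precision target or an expected outlier rate, so there is no ECG figure to reproduce. The sizes below rest on assumptions.

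**Assumed inputs.** Between-patient SD τ = 15 msec; single-reading within-patient SD s = 8 to 15 msec, with half of its variance shared by readings at the same visit; QTcF stable over time without treatment; one on-study ECG per patient. The last is a reasonable simplification under the supplied protocol. Its on-study ECGs are all pre-infusion in week 1 of a cycle, and the pre-dose PK samples fall at C1W3, C2W1 and C2W3, so C2W1 is the only on-treatment ECG with a matching concentration.

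**Formulas.**
- No baseline term: variance of change = 2s².
- Single-reading baseline as covariate: τ² + s² − τ⁴/(τ² + s²).
- Three-reading mean as covariate: τ² + s² − τ⁴/(τ² + n·s²). The two screening readings share visit error with total weight 2/3 and Day 1 has weight 1/3. The visit half therefore contributes (4/9 + 1/9)/2 and the replicate half (1/3)/2, giving n = 0.444.

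**Example, s = 10.** 2 × 100 = 200. Then 325 − 50,625/325 = 169. Then 325 − 50,625/269.4 = 137.

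| s (msec) | No term | One-reading covariate | Cut | Three-reading covariate | Further cut | Both |
|---|---|---|---|---|---|---|
| 8 | 128 | 114 | 11% | 89 | 22% | 30% |
| 10 | 200 | 169 | 15% | 137 | 19% | 31% |
| 12 | 288 | 232 | 20% | 194 | 16% | 33% |
| 15 | 450 | 337.5 | 25% | 294 | 13% | 35% |

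Interval width goes with the square root of variance. For the covariate alone, 1 − √0.889 = 6% and 1 − √0.75 = 13%. For the averaging step, 1 − √0.872 = 7% and 1 − √0.784 = 12%.

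**Chance imbalance in msec (40 per arm, Protocol 10.2; s = 10).** The baseline SD is √325 = 18.0, so the standard error of the baseline difference is 18.0 × √(2/40) = 4.0. The slope of change on baseline is −100/325 = −0.31. A one-standard-error imbalance therefore moves the unadjusted contrast by about 0.31 × 4.0 = 1.2 msec, in either direction.

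**False rises above 30 msec at one time point, no drug effect.** The rate is 1 − Φ(30/(s√(1 + n))), with n = 1 for one reading and 0.444 for the mean of three.

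| s (msec) | One reading | Mean of three | Ratio |
|---|---|---|---|
| 8 | 0.40% | 0.09% | 4.4 |
| 10 | 1.7% | 0.63% | 2.7 |
| 12 | 3.9% | 1.9% | 2.1 |
| 15 | 7.9% | 4.8% | 1.6 |
| 20 | 14.4% | 10.6% | 1.4 |

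Letting the visit share run from none to all (n from 1/3 to 5/9), the ratio over SD 8 to 20 runs from about 1.3 to about 7. Absolute thresholds do not use the baseline, so their counts do not change. The missing model term affects no outlier count.

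**The case against.** **No bias.** Regression to the mean acts alike in both arms in expectation, the arms are randomised, and the target is placebo-corrected. A reader might infer that the exposure-response estimate is systematically wrong; the documents do not support that. What remains is precision and chance imbalance, and neither document sets an ECG margin, test or power target against which the loss would be decisive. This stands.

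**No single percentage fits all ECG contrasts.** A reader might infer that they all lose about 30% of obtainable precision. That figure is on the variance scale and needs both changes in the exposure-response contrast. The by-timepoint model already has the covariate and can gain only from averaging. Nor are the figures the variance of the model's own output: they come from a two-arm contrast with one ECG, without the concentration slope, the random effects or the prediction at Cmax. This stands too.

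**No general doubling of false outliers.** The ratio is near two only for some assumed SDs and only for change-from-baseline counts.

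**Day 1.** Read alone, the wording of SAP 3.6.2 could exclude the Day 1 pre-infusion ECG and place it in Cycle 1, so a reader might infer that untreated ECGs are analysed as on-treatment. SAP 3.8 allows a pre-dose Day 1 value, and the by-timepoint model takes its repeated measures at post-dose time points. The text needs a clarifying cross-reference; it is not a demonstrated error.

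**Averaging is debatable.** Protocol 6.1 times the screening ECG from main consent, so it may fall outside the SAP's 28-day window. Standard systemic therapy may also continue until 14 days before dosing (Protocol 4.2), so screening readings may represent the pre-dose state less well. Closest-to-dose is a defensible choice. This makes averaging secondary and does not touch the missing covariate.

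**Different studies.** The reading schedule and the 80 patients come from MM-121-02-02-10. The ECG schedule of the study that the SAP names was not supplied. The inconsistency between the two models lies wholly within the SAP and does not depend on this; the count of three readings does.

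**Conclusion.** The point holds as a modest improvement at almost no cost. Under the assumptions above, the missing covariate is worth about 11 to 25% of residual variance in a simplified exposure-response contrast, equivalent to about 13 to 33% more patients (1/0.889 to 1/0.75). Averaging is a separate and weaker recommendation. It offers the by-timepoint model its only gain, about 7 to 12% in interval width, and reduces false rises above 30 msec by a factor that cannot be fixed without the SD. The direction of these gains is secure if untreated QTcF is stable between screening and dosing; their size is not known from the documents.

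**What to change.** In SAP 5.6.5, add baseline QTcF as a covariate to the exposure-response model, matching the by-timepoint model. The cost is one model term.

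Secondary, in SAP 3.6.2: consider defining the ECG baseline as the mean of all valid readings before the first infusion within the 28-day window. In line with SAP 3.8, state that a pre-infusion Cycle 1 Day 1 ECG counts as baseline and not as on-treatment. The cost is a small derivation change, plus the drawback that screening readings may be less representative of the state just before dosing.

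State which protocol's ECG schedule the section applies to, since the SAP names 02-03-10 and the supplied protocol is MM-121-02-02-10. None of this needs new data or procedures, and the absolute QTcF thresholds can stay as written.
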